16.6 Columbia-Suicide Severity Rating Scale (C-SSRS)

Suicidality will be monitored during the study using the C-SSRS. The C-SSRS is a questionnaire used to measure the presence and intensity of suicidal ideation and behavior. The C-SSRS will be completed at Screening, Days -7, -1, 1, 7, 14, and 28 for Part A, and additional Day 21, Day 35, and Day 42 are completed for Part B. The "Baseline/Screening" C-SSRS form will be completed at screening (lifetime history and past 24 months). The "Since Last Visit" C-SSRS form will be completed at subsequent time points.

Suicidal behavior and suicidal ideation will be summarized by visit for the Safety analysis set. The proportion of participants who meet the criterion for each of these categories at any post-baseline visit will be summarized as described in Table 8.

Table 8 C-SSRS Categories for Analysis

Category	C-SSRS Item response is “YES”
Suicidal ideation	
 • Wish to be dead • Non-specific active suicidal thoughts • Active suicidal ideation with any methods (not plan) without intent to act • Active suicidal ideation with some intent to act, without specific plan • Active suicidal ideation with specific plan and intent
Suicidal behavior	
 • Actual attempt • Interrupted attempt • Aborted attempt • Preparatory acts or behavior • Completed suicide ^[1]
Non-suicidal self-injurious behavior	
 • Non-suicidal self-injurious behavior

^[1] Completed suicide is not collected at the screening visit.

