6.2.2. Secondary Endpoint

The secondary endpoint of this study will be assessed as the change from baseline in vital signs, clinical laboratory analytes, electrocardiograms (ECGs), and responses on the Columbia–Suicide Severity Rating Scale (C-SSRS).

[REDACTED]

- [REDACTED]
- [REDACTED]
- [REDACTED]
- [REDACTED]
- [REDACTED]
- [REDACTED]
- [REDACTED]

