 - d. Other medications given at doses, frequencies, or in combinations that are likely, in the opinion of the investigator, to have a deleterious effect on cognitive performance, based on the 2019 American Geriatrics Society Updated Beers[®] Criteria for

Potentially Inappropriate Medication Use in Older Adults ([American Geriatrics Society 2019](#))

- e. Prescribed cannabis or other THC-containing substances
12. Have an alcohol or drug use disorder within the past 12 months as per DSM-5 criteria
 13. Have a history of seizures or epilepsy, with the exception of a single episode of febrile seizures in childhood
 14. Have current or recent suicidality, defined as follows:
 - a. Suicidal ideation within the past month, as evidenced by a score of 4 (active suicidal ideation with some intent to act, without specific plan) or 5 (active suicidal ideation with specific plan and intent) on the screening or baseline Columbia–Suicide Severity Rating Scale (C-SSRS)
 - b. Suicidal behavior within the past year, as evidenced by a "Yes" on any of the 5 C-SSRS Suicidal Behavior Items (actual attempt, interrupted attempt, aborted attempt, preparatory acts, or behavior) on the C-SSRS during Screening or Baseline
 - c. Participant presents a serious risk of suicide in the opinion of the investigator.
 15. Have any of the following clinically significant medical conditions:
 - a. Any clinically significant finding on 12-lead ECG during Screening or Baseline
 - b. Supine vital signs outside of the following ranges during Screening or Baseline; vital sign measurements may be repeated once if initial values exceed these ranges:
 - Heart rate <50 or >100 bpm
 - Systolic blood pressure <100 or >160 mmHg
 - Diastolic blood pressure <60 or >100 mmHg
 16. Have significant hepatic, renal, cardiovascular, pulmonary, gastrointestinal, hematological, immunologic, ophthalmologic, metabolic, or oncological disease
 17. Have a history, presence, and/or current evidence of serologic positive results for HIV-1 or HIV-2
 18. Have a positive pregnancy test or be lactating at Screening or Day -1
 19. Be investigative site personnel, sponsor personnel, or an immediate member of their family (spouse, parent, child, or sibling whether biological or legally adopted)

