12.1.7.3. Columbia–Suicide Severity Rating Scale

Suicidality will be monitored during the study using the C-SSRS (Paul 2011). This scale consists of a baseline evaluation that assesses the lifetime experience of the participant with suicidal ideation and behavior, and a postbaseline evaluation that focuses on suicidality since the last study visit. The C-SSRS includes ‘yes’ or ‘no’ responses for assessment of suicidal ideation and behavior as well as numeric ratings for severity of ideation, if present (from 1 to 5, with 5 being the most severe).

The “Baseline/Screening” C-SSRS form will be completed at Screening (lifetime history and past 24 months). The “Since Last Visit” C-SSRS form will be completed at all subsequent time points outlined in [Table 2](#) and [Table 4](#).

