13.6. Safety Analyses

Safety and tolerability of SAGE-718 will be evaluated by TEAEs and change from baseline in vital signs, clinical laboratory analytes, ECGs, and responses on the C-SSRS. Safety data will be listed by participant and summarized by treatment group. All safety summaries will be performed on the Safety Set.

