13.6.7. Columbia–Suicide Severity Rating Scale

Suicidality data collected on the C-SSRS at Baseline and by visit during the Treatment Period will be listed and summarized for all participants. Listings will include behavior type and/or category for Suicidal Ideation and Suicidal Behavior of the C-SSRS.

[REDACTED]

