9.2 Secondary Endpoints

- Change from baseline in vital signs, clinical laboratory analytes, and electrocardiograms (ECGs).
- Responses on the Columbia–Suicide Severity Rating Scale (C-SSRS).

[Redacted text block containing multiple paragraphs and bulleted lists, all obscured by black boxes.]

[Redacted text block containing several paragraphs and bullet points]

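### The SAP plans no within-participant change analysis for the C-SSRS, although the protocol's secondary endpoint is change from baseline, and it does not declare the difference

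*SAP*

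**What the plan says.** **Protocol**

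- Section 6.2.2: the secondary endpoint "will be assessed as the change from baseline in vital signs, clinical laboratory analytes, electrocardiograms (ECGs), and responses on the" C-SSRS. Section 13.6 uses the same list: safety is judged by TEAEs and "change from baseline in vital signs, clinical laboratory analytes, ECGs, and responses on the C-SSRS".
- Section 12.1.7.3: the scale yields yes/no answers and "numeric ratings for severity of ideation, if present (from 1 to 5, with 5 being the most severe". The form used at Screening looks back over the lifetime and the past 24 months. Every later form covers the time since the last visit.
- Section 8.2, criterion 14a, excludes "Suicidal ideation within the past month, as evidenced by a score of 4" or 5. Levels 1 to 3 are not excluded by score, although 14c lets the investigator exclude anyone judged at serious risk.
- Section 13.6.7: "Suicidality data collected on the C-SSRS at Baseline and by visit during the Treatment Period will be listed and summarized for all participants". It defines no change or shift.

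**SAP**

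- Section 9.2 gives one bullet to "Change from baseline in vital signs, clinical laboratory analytes, and electrocardiograms (ECGs") and a separate bullet to C-SSRS responses, with no mention of change.
- Section 6.1 declares one departure from the protocol, an added summary table for medications.
- Section 16.0 still places C-SSRS responses in its change-from-baseline list. It defines the safety baseline as the last non-missing value before the first dose.
- Section 16.6 plans a summary of ideation and behavior by visit, and adds: "The proportion of participants who meet the criterion for each of these categories at any post-baseline visit will be summarized". Table 8 groups five ideation items under one category, the criterion being that the item is answered yes.
- Appendix G lists one C-SSRS summary table per Part (14.3.6A and 14.3.6B) and Listing 16.2.12. It lists no shift or worsening table.

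**The concern.** The protocol names an endpoint that needs each participant's post-baseline response set against that participant's own baseline. The SAP, where the method should be supplied, gives only proportions. The C-SSRS has an ordered ideation level that would support a change analysis, and people with mild ideation may enter, so change from a non-zero baseline is possible by design.

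At stake is whether the tables for this part of the secondary safety endpoint can tell persisting mild ideation from ideation that became more severe on drug. If they cannot, unchanged ideation counts as a post-baseline finding, and a rise in severity adds nothing to the category count.

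**Working it through.** The plan states no figure on this point, so there is none to reproduce. The check sets the sections side by side and then follows what the planned count does.

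**1. Endpoint against method**

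| Component | Protocol 6.2.2 | SAP 9.2 | Change method in the SAP |
|---|---|---|---|
| Vital signs | change | change | 16.4: change by time point; change criteria in Table 6 |
| Laboratory analytes | change | change | 16.2: change by visit |
| ECG | change | change | 16.5: change by time point; QTcF change criteria in Table 7 |
| C-SSRS | change | responses only | none in 16.6 |

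The C-SSRS is the only component without a change method.

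**2. Which rises are possible.** Eligible recent baseline levels are 0 to 3 and post-baseline levels 0 to 5, which gives 4 × 6 = 24 cells. Upward moves number 5 + 4 + 3 + 2 = 14. Of these, 4 + 3 + 2 = 9 start from levels 1 to 3, and 3 × 2 = 6 of the nine end at level 4 or 5. If the ideation category means any item answered yes, none of the nine is separated from unchanged ideation. These are counts of cells, not of likely events.

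**3. What the count does.** Assume k participants enter at level 2 and still report ideation after baseline, and m of them rise to level 5. The remaining participants stay at 0.

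| k | Any-yes count, Part A (n = 11) | Any-yes count, Part B (n = 22) | Count of increases |
|---|---|---|---|
| 1 | 1 (9.1%) | 1 (4.5%) | m, from 0 to 1 |
| 2 | 2 (18.2%) | 2 (9.1%) | m, from 0 to 2 |
| 3 | 3 (27.3%) | 3 (13.6%) | m, from 0 to 3 |

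The any-yes count is k for every m. This holds while ideation persists; a participant whose ideation stops leaves the count.

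**4. Can a size be given?** Let p be the share entering at levels 1 to 3, w their chance of worsening, and e the chance of new ideation in the rest. The chance that at least one rise reaches the table is

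- any-yes count: 1 − (1 − (1 − p)e)^n
- full scale: 1 − (1 − (1 − p)e − pw)^n

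With assumed p = 0.2, w = 0.2, e = 0.02 and n = 22, these are 1 − 0.984^22 = 30% and 1 − 0.944^22 = 72%. Over assumed ranges p = 0.1 to 0.3, w = 0.1 to 0.2 and e = 0.02 to 0.05, the difference runs from 8 to 55 points at n = 22 and from 7 to 43 at n = 11. The documents give none of these rates. The formula also credits the any-yes count with showing new ideation, which that count does not separate from persisting ideation. So wide a range on unsupported inputs is not a usable size.

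**5. Which baseline a change analysis would use**

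- The last non-missing value would be the Day 1 form if completed before dosing. That form looks back only to Day -1.
- The maximum over all pre-dose forms takes in the Screening form. Criterion 14a bars levels 4 and 5 only in the past month, so an eligible participant with an older level 5 could never register a rise.
- The maximum over the since-last-visit forms between Screening and the first dose (Day -7, Day -1, and Day 1 if pre-dose) covers roughly one to three weeks, because Screening falls between Day -21 and Day -8. It avoids both problems.

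**The case against.** The other side has five fair arguments.

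- **Table 8 does not say that any one item suffices.** It lists the items separately, and its footnote on completed suicide at Screening concerns a single item, which hints at item rows. The table shells are not given. This stands: collapsing to any yes is the natural reading, because the proportion is taken per category, but it is not explicit. With item rows, a post-baseline yes on item 4 or 5 would be visible and would lie above the past-month level allowed at entry. A move from 1 to 2, 1 to 3 or 2 to 3 still could not be tied to a participant.
- **Other outputs exist.** The by-visit summary is planned, Listing 16.2.12 can be read by hand for up to 33 people, and clinically important worsening could also be reported as an adverse event. This stands as well. A reader might infer that worsening cannot be seen at all, and the documents do not support that. By-visit proportions are marginal, however: one participant improving and another worsening can leave them unchanged.
- **Protocol 13.6.7 defines no change analysis either.** True. The gap begins in the protocol, and the SAP carries it forward.
- **SAP 16.0 keeps the change wording.** True, so the SAP is inconsistent with itself rather than silent. No method follows from 16.0.
- **A shift table adds little in a small, uncontrolled, descriptive study.** The table will be sparse, but it is the direct summary of the endpoint that the protocol names.

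**Conclusion.** The point holds as a mismatch between endpoint and planned summary. The protocol asks for change from baseline in C-SSRS responses. SAP 9.2 drops this without declaring it in SAP 6.1, and SAP 16.6 supplies no level, shift, new-onset or worsening rule. As specified, the summaries do not show within-participant change, so a participant who enters at level 1 to 3 and rises is not separated from one who stays the same except by reading the listing.

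The gap is in the summary, not in data capture or in monitoring of participants. A reader might take 9 of 14 upward moves (64%) as the share of worsening that would be missed. That treats all cells as equally likely, which nothing in the documents supports. The 30% against 72% comparison rests wholly on assumed rates. No reliable size can be given.

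The conclusion assumes the natural reading of Table 8. Under item rows it narrows, because levels 4 and 5 would appear marginally, but the missing change analysis remains.

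**What to change.** 1. In SAP 9.2, restore change from baseline for the C-SSRS, in line with Protocol 6.2.2 and SAP 16.0. If the sponsor means to drop it, SAP 6.1 should say so.
2. In SAP 16.6 and Tables 14.3.6A/B, add one shift table per Part: baseline ideation level (0 to 5) by maximum post-baseline ideation level (0 to 5). Report three counts: new ideation (0 to 1 or more), any increase, and increase to level 4 or 5.
3. Name the baseline as a recent pre-dose level, for example the maximum over the since-last-visit forms completed between Screening and the first dose. State it as a C-SSRS-specific exception to the last-non-missing rule.
4. Show lifetime and 24-month Screening history separately, so that it cannot hide worsening.
5. Keep the Table 8 proportions, and state whether the ideation row means any item or whether items are tabulated singly.

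The cost is SAP wording and one small table per Part from data already collected. Most cells will be empty at 11 and 22 participants. If the database is already locked, SAP 6.0 provides for describing and justifying the change in the clinical study report.

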16.7 Electroencephalogram (EEG)

During Screening, EEG monitoring using the 10 to 20 international system for EEG electrode placement will occur for a duration of 1 hour. The assessment may be performed on any single day during the Screening Period, at any time of day, but preferably while the participant is in a fed state. If clinical events suspicious for seizure occur after Screening (eg, episodes of altered consciousness and/or involuntary motor behaviors), an unscheduled 1-hour EEG will be performed for safety. EEG will be listed by the participant.

18.0 Glossary of Abbreviations

Glossary of Abbreviations:	
AE	Adverse event
ATC	Anatomic Therapeutic Chemical
AUC _{0-t}	Area under the plasma concentration-time curve, from time 0 to time t
AUC _{0-last}	Area under the curve from the time of dosing to the time of the last measurable (positive) concentration
BLQ	Below the Limit of Quantification
CI	Confidence Interval
CV	Coefficient of Variation
C _{max}	Maximum observed concentration.
COVID-19	Coronavirus Disease 2019
CRF	Case Report Form
CSR	Clinical Study Report
ECG	Electrocardiogram
eCRF	Electronic Case Report Form
FAS	Full Analysis Set
IP	Investigational Product
LLOQ	Lower Limit of Quantification
MedDRA	Medical Dictionary for Regulatory Activities
PCS	Potentially Clinically Significant
PT	MedDRA Preferred Term
Q1	First Quartile
Q3	Third Quartile
SAP	Statistical Analysis Plan
SAE	Serious Treatment-emergent Adverse Event
SI	International System of Units
SOC	MedDRA System Organ Class
Std	Standard Deviation
TEAE	Treatment Emergent Adverse Event
WHO	World health Organization
WPAI:GH	Work Productivity and Activity Impairment: General Health

19.0 Appendix

19.1 Appendix-A Schedule of Study Assessments (Part A)

Study Period	Screenin g	Baseline		Treatment			Follow Up		
	D -21 to D -8	D -7 (±1 d)	D -1	D 1	D 4 ^a	D 7 (±1 d)	D 14 or ET	D 21 ^a (±1 d)	D 28 (±2 d)
Informed consent ^b	X								
Inclusion/exclusion criteria	X	X	X						
Medical history and demographics ^c	X								
Bodyweight	X			X		X	X		X
Body height	X								
Hoehn and Yahr staging	X								
Montreal Cognitive Assessment	X								
Test of Premorbid Functioning	X								
Vital signs ^d	X	X	X	X		X	X		X
Physical examination ^e	X	X	X				X		
EEG ^f	X								
12-lead ECG ^g	X		X	X		X	X		X
C-SSRS ^h	X	X	X	X		X	X		X
Clinical laboratory tests ⁱ	X		X			X	X		X
Alcohol test ^j	X	X							
Urine drug test	X	X	X	X		X	X		
FSH test ^k	X								
Pregnancy test ^l	X		X				X		X
Serology test ^m	X								
Participant training ^o		X	X						

Study Period	Screening	Baseline		Treatment				Follow Up	
Study Day	D -21 to D -8	D -7 (±1 d)	D -1	D 1	D 4 ^a	D 7 (±1 d)	D 14 or ET	D 21 ^a (±1 d)	D 28 (±2 d)
Remote assessments ^t				X					
IP self-administration ^u				X (once daily)					
IP dispensation ^v				X		X			
IP accountability ^w				X					
Safety telephone call					X			X	
TEAEs/SAEs				X					
Concomitant medications ^x				X					

Abbreviations: C-SSRS = Columbia–Suicide Severity Rating Scale; d = days; ECG = electrocardiogram; EEG = electroencephalogram; ET = early termination; FSH = follicle stimulating hormone; IP = investigational product; SAE = serious adverse event; TEAE = treatment-emergent adverse events;

Note: In the event of early termination, efforts should be made to collect the Day 14 visit assessments. When scheduled for the same time point, procedures should be performed in the following order: vital signs, ECG, blood draws, morning meal, IP dosing, then any scheduled postdose and/or

In the setting of public health advisories or similar risks to patient safety, assessments scheduled to be conducted at the study site may be performed via telephone/video if feasible. For assessments that cannot be conducted by phone or video, an in-home visit may be conducted.

a Day 4 and Day 21 visits will occur via scheduled telephone calls.

b Both participants and caregivers are to be consented during the Screening Period.

c In addition to full medical history, all nonpharmacological methods (eg, psychosocial, psychotherapeutic) used to treat or prevent neuropsychiatric, functional, and cognitive manifestations of PD are to be recorded.

d Vital signs to include temperature, respiratory rate, heart rate, and blood pressure. Heart rate and blood pressure to be collected in supine position and standing position at all scheduled time points. When scheduled for the same visit, vital signs are to be assessed prior to ECG and blood collection.

e A full physical examination is to be conducted during Screening. Thereafter, physical examinations will include a brief assessment of general appearance, cardiovascular, respiratory, gastrointestinal, and

neurological systems and followed by a targeted physical assessment as needed. A symptom-directed examination may be conducted at any time at the discretion of the investigator.

f An EEG will be performed for all participants at any time of day during Screening, preferably in a fed state. Subsequently, if the investigator or study staff become aware of events suspicious for seizure, an unscheduled 1-hour EEG will be performed for that participant. A second, follow-up, 1-hour EEG may be performed at the discretion of the investigator.

g ECG will be measured after the participant has been in the supine position for at least 5 minutes.

h "Baseline/Screening" C-SSRS form at Screening and "Since Last Visit" C-SSRS form thereafter.

i Clinical laboratory assessments to include blood samples for hematology, biochemistry, coagulation, urinalysis, and serology, are to be collected ≤ 2 hours prior to dosing during the Treatment Period, and any time of day at other time points. Participants are to be in a fasted state for screening assessments only.

j Alcohol testing will be performed in the clinic, either by urine dipstick or breathalyzer.

k To confirm self-reported postmenopausal status in women only.

l Serum pregnancy tests for all female participants at Screening; urine pregnancy tests will be conducted for all female participants who are not postmenopausal or surgically sterile at other scheduled time points.

m To include testing for hepatitis B and C, HIV 1, and HIV 2

[REDACTED]

o Participants and caregivers will be trained to use all study-related software and devices. Additional guidance will be provided on choosing a meal with approximately 30 g of fat.

[REDACTED]

[REDACTED]

[REDACTED]

[REDACTED]

t Daily reminders will be sent to participants via a mobile device to complete assessments of [REDACTED] [REDACTED] (see Section 14.1) within 1 hour following IP administration either remotely (at home) or in the clinic under observation by the study staff.

u On visit days during the Treatment Period, participants will self-administer IP in the clinic under the supervision of study staff after the predose assessments and consumption of a morning meal.

v Study staff will dispense sufficient IP for daily dosing at home until the next scheduled visit.

w On Days 7 and 14, participants will return used IP packaging and any unused IP for site staff to document.

x At Screening, to include all medications and supplements taken within 60 days and all medications used to treat PD regardless of timing. At visits subsequent to Screening, all changes to any medication should be captured

19.2 Appendix-B Schedule of Study Assessments (Part B)

Study Period	Screening	Baseline		Treatment						Follow Up	
		D -21 to D -8	D -7 (±1 d)	D -1	D 1	D 4 ^a	D 7 (±1 d)	D 14 (±1 d)	D 21 (±1 d)	D 28 or ET	D 35 (±1 d)
Informed consent ^b	X										
Inclusion/exclusion criteria	X	X	X								
Medical history and demographics ^c	X										
Bodyweight	X			X		X	X	X	X	X	X
Body height	X										
Hoehn and Yahr staging	X										
Montreal Cognitive Assessment	X										
Test of Premorbid Functioning	X										
Vital signs ^d	X	X	X	X		X	X	X	X	X	X
Physical examination ^e	X	X	X						X		
EEG ^f	X										
12-lead ECG ^g	X		X				X		X		X
C-SSRS ^h	X	X	X	X		X	X	X	X	X	X
Clinical laboratory tests ⁱ	X		X				X		X		X
Alcohol test ^j	X	X									
Urine drug test	X	X	X	X		X	X	X	X		
FSH test ^k	X										
Pregnancy test ^l	X		X				X		X		X
Serology test ^m	X										

Study Period	Screening	Baseline		Treatment						Follow Up	
Study Day	D -21 to D -8	D -7 (±1 d)	D -1	D 1	D 4 ^a	D 7 (±1 d)	D 14 (±1 d)	D 21 (±1 d)	D 28 or ET	D 35 (±1 d)	D 42 (±2 d)
Participant training ^o		X	X								
Remote assessments ^t	X										
IP self-administration ^u				X	X	X	X	X	X		
IP dispensation ^v				X		X	X	X			
IP accountability ^w						X	X	X	X		
Safety telephone call					X						
TEAEs/SAEs	X										
Concomitant medications ^x	X										

Note: In the event of early termination, efforts should be made to collect the Day 28 visit assessments. When scheduled for the same time point, procedures should be performed in the following order: vital signs, ECG, blood draws, morning meal, IP dosing, then any scheduled postdose and/or [REDACTED]. In the setting of public health advisories due to COVID-19 or similar risks to patient safety, assessments scheduled to be conducted at the study site may be performed via telephone/video if feasible. For assessments that cannot be conducted by phone or video, an in-home visit may be conducted.

a Day 4 visit will occur via scheduled telephone call.

b Both participants and study partners are to be consented during the Screening Period.

c In addition to full medical history, all nonpharmacological methods (eg, psychosocial, psychotherapeutic) used to treat or prevent neuropsychiatric, functional and cognitive manifestations of PD are to be recorded.

d Vital signs to include temperature, respiratory rate, heart rate, and blood pressure. Heart rate and blood pressure to be collected in supine position and standing position at all scheduled time points.

e A full physical examination is to be conducted during Screening. Thereafter, physical examinations will include a brief assessment of general appearance, cardiovascular, respiratory, gastrointestinal, and neurological systems and followed by a targeted physical assessment as needed. A symptom-directed examination may be conducted at any time at the discretion of the investigator.

f An EEG will be performed for all participants at any time of day during Screening, preferably in a fed state. Subsequently, if the investigator or study staff become aware of events suspicious for seizure, an unscheduled 1-hour EEG will be performed for that participant. A second, follow-up, 1-hour EEG may be performed at the discretion of the investigator.

g ECG will be measured after the participant has been in the supine position for at least 5 minutes.

h "Baseline/Screening" C-SSRS form at Screening and "Since Last Visit" C-SSRS form thereafter.

i Samples for clinical laboratory assessments, to include blood samples for hematology, biochemistry, coagulation, urinalysis, and serology, are to be collected ≤ 2 hours prior to dosing during the Treatment Period, and any time of day at other time points. Participants are to be in a fasted state for screening assessments only.

j Alcohol testing will be performed in the clinic, either by urine dipstick or breathalyzer.

k To confirm self-reported postmenopausal status in women only.

l Serum pregnancy tests for all female participants at Screening; urine pregnancy tests will be conducted for all female participants who are not postmenopausal or surgically sterile at other scheduled time points.

m To include testing for hepatitis B and C, HIV-1, and HIV-2

[REDACTED]

o Participants and study partners will be trained to use all study-related software and devices. Additional guidance will be provided on choosing a meal with approximately 30 g of fat.

[REDACTED]

[REDACTED]

[REDACTED]

[REDACTED]

t Daily reminders will be sent to participants via a mobile device to complete assessments of [REDACTED] (see Section 14.1) within 1 hour following IP administration either remotely (at home) or in the clinic under observation by the study staff.

v On visit days during the Treatment Period, participants will self-administer IP in the clinic under the supervision of study staff after the predose assessments and consumption of a morning meal.

w Study staff will dispense sufficient IP for daily dosing at home until the next scheduled visit.

y At clinic visits during the Treatment Period, participants will return used IP packaging and any unused IP for site staff to document.

x At Screening, to include all medications and supplements taken within 60 days and all medications used to treat PD regardless of timing. At visits subsequent to Screening, all changes to any medication should be captured.

